## 5.0 Study Design

To fulfill the purposes outlined above, a 2-arm randomized controlled study design will be employed. After completing initial screening procedures (**screening visit**), subjects will return

to the School of Public Health at Indiana University Bloomington to have baseline measures of weight, body composition, bone density, heart rate, cutaneous vascular conductance, blood pressure, assessed prior to and 3-hours following ingestion of beetroot juice (**Visit 1**). During this visit, two questionnaires will be administered to obtain information related to the health history, physical activity habits, mood state, and cognitive abilities of the subjects. Following a minimum 7-day washout period, to mitigate the risk of any carry-over effect from the acute dose of beetroot juice administered during the initial visit, subjects will have their blood drawn at the Indiana University Student Health Center followed by measures of weight, body composition, and pulse wave velocity performed at the School of Public Health at Indiana University Bloomington (**Visit 2**). During this visit they will also perform two 6-minute walking tests, and muscle function test. After baseline assessments **Visits 1-2**, participants will be randomly assigned to one of two study arms. All study arms will complete an 8-week exercise training protocol. The first arm will serve as a control group and will require participants to only complete the 8-week exercise training protocol (EX). The second arm will complete exercise training with ingestion of a beetroot (BR+EX). Exercise training will occur no more than 6 weeks following baseline Visit 2 to minimize the effects of potential changes in physical conditioning/deconditioning on baseline measures. Subjects will be asked to repeat baseline Visit 2 before initiating exercise training in the event >6 weeks lapses from the completion of the final baseline assessment visit.

The same procedures as performed in **Visits 1-2** will be repeated following the treatment intervention for **Visits 3-4** in reverse order. The procedures outlined for **Visit 2** will be performed during **Visit 3**, and procedures for **Visit 1** for **Visit 4**.

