## 6.0 Enrollment/Randomization

The present study will rely on participant self-referral in response to recruitment materials. Participants will be recruited from the local community through approved flyers and/or approved written scripts (See Attachments) via:

- social media
- newspaper ads
- physical postings with permission from local establishments
- or sent to the email address of local organizations with the intent that the approved recruitment flyer will be forwarded to a member of their organization. Additionally, study details will be registered through the Indiana CTSI All IN for Health website. Open recruitment will occur for fixed periods (4-6 weeks).

Additional recruitment efforts include referral from the Indiana CTSI All IN for Health Volunteer Registry.

Subjects will be identified from the Indiana CTSI volunteer registry Protocol Number 1105005444. This website is created for interested individuals to contact us and sign up to receive information about ongoing studies and is supported by the Indiana CTSI. Persons in this registry have provided their health information for the purposes of being matched to appropriate research studies. The registry volunteers have signed an electronic consent/authorization so that their information can be used and they can be contacted for this reason.

The All IN manager will send an email message (see provided email text) to participants describing the study and asking them to reach out to the study team directly if they are interested in hearing more about the study.

Individuals expressing interest in the study will contact research personnel by telephone and /or email. If, by email, an agreed upon time to speak over the phone will be determined. During the phone call, research personnel will adhere to a scripted telephone screen wherein additional information detailing the inclusion/exclusion criteria, study procedures, requirements, and risks will be covered.

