Participants will perform baseline assessments (**Visits 1-2**) prior to randomization. Subsequently, participants will be randomly selected to: 1) control (EX only) or 2) BR+EX. Group allocation will be determined at random using a computer-based number generator in blocks of 2 to ensure equal between-group distribution (i.e.  $n = 2$  Ex only;  $n = 2$  BR+EX). Each number will be kept in a sealed envelope until completion of **Visits 1-2**.

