standard set of hospital scrubs so that accurate measurements of body weight (BIA) and composition (BIA) can be obtained. They will then be asked to lie supine while resting quietly for a period of 10 minutes on a padded table while measures of pulse wave velocity are obtained. They will then be escorted to the recreational track within the School of Public Health building to complete the 6-min walking test and muscle function test.

(8-weeks Supervised Exercise Training) After being randomized into either an exercise only (EX) or beetroot and exercise (BR+EX) group, subjects in the BR+EX group will receive a 4-week supply of beetroot juice. They will additionally be asked to attend 3 sessions of supervised exercise training at CrossFit, Bloomington for a duration of 8 weeks. Subjects in BR+EX will be instructed to consume the beetroot juice 3 hours prior to each attended exercise session.

(Visits 2-3) The remaining follow-up visits will follow the exact same procedures as outlined for Visits 1-2 and will be performed in the reverse order.

	Screening	Initial Assessments		Exercise Training Intervention	Follow-up Assessments	
	Time point 0	Visit 1 (as scheduled)	Visit 2 (following  7-day washout period)	0 to 8 weeks (following £ 6 weeks)	Visit 1 (following  2 days)	Visit 2 (following  2 days)
STUDY PROCEDURES						
Obtain Consent	X					
Medical History Questionnaire	X					
ACSM Risk Factor Stratification	X					
Obtain Permission to Contact Physician	X					
Verification of Age (driver's license)	X					
Prescription Medication Verification	X					
Height	X	x				X
Body Weight (BIA)	X	x	X		X	X
Body Fat Percentage (BIA)		X	X		X	X
Total Body Water (BIA)		X	X		X	X
DEXA		X				X
Heart rate (Actiheart)		X		X		X
Localized Heating Protocol using Laser Doppler		X				X
Blood Pressure		X				X
Nitric Oxide Breath Analysis		X		X		X
Acute Administration of Beetroot Juice (140 mL)		X				X
Blood Oxygen/ Methemoglobin Oximetry		X				X
Questionnaire (Part A and B)		X				X
Venous Blood Draw			X		X	
Pulse Wave Velocity			X		X	
Submaximal Walk Test			X		X	
Heart rate (chest-strap)			X		X	
Accelerometry			X		X	
6-minute Walk Test			X		X	

Rates of Exertion (continuous analog scale)			X		X	
Rates of Exertion (discrete analog scale)			X	X	X	
Isokinetic Dynamometry			X		X	
Supervised Exercise Training Sessions				X		
24hr Dietary Recall				X (3 during week 1 and 3 during week 8 of supervised exercise training)		

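### The plan lets a repeat baseline Visit 2, including the 6-minute walk, take place after the arm is known, and does not say which Visit 2 is the analysis baseline

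*Combined protocol and SAP*

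**What the plan says.** **Order and concealment.** Section 5.0 (Study Design) places allocation after the baseline visits: "participants will be randomly assigned to one of two study arms". Section 6.0 (Enrollment/Randomization) gives the same order and adds the concealment rule: "Each number will be kept in a sealed envelope until completion of" Visits 1-2. It gives no date for opening.

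**Repeat rule.** Section 5.0 limits the wait: "Exercise training will occur no more than 6 weeks following baseline Visit 2". If the limit is passed, "Subjects will be asked to repeat baseline Visit 2 before initiating exercise training in the event >6 weeks lapses", counted "from the completion of the final baseline assessment visit".

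**Masking.** Section 5.0 describes the comparator as follows: "The first arm will serve as a control group and will require participants to only complete the 8-week exercise training protocol (EX"). No placebo drink is described, and no section describes masking of participants or assessors. Section 8.0 (Study Calendar) says that after randomisation "subjects in the BR+EX group will receive a 4-week supply of beetroot juice". It does not place the hand-out before or after a repeat Visit 2.

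**Use of the baseline.** Section 3.2 names 6-minute walk distance as the main secondary outcome and judges it from baseline to post-intervention, BR+EX against EX. Section 12.0 compares the arms with an unpaired t-test and reports Cohen's d. Neither section says which Visit 2 counts when there are two.

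**The concern.** A baseline is safe in a comparison of change because it is measured before anyone can know the arm. Here the rule that protects that order ends at the first Visit 2, while the repeat rule can call for another one at least six weeks later. Walking distance and maximal knee extension, both measured at Visit 2, depend on effort and on encouragement. A woman who knows she will, or will not, receive the juice may walk differently, and so may the encouragement given by a tester who knows. Any such shift enters the change score directly, and its sign cannot be predicted.

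The stated purpose of Aims 2 and 3 is to supply preliminary effect sizes for a larger study, so a bias in d would carry into that study's planning. Leaving the choice of baseline open adds a second problem: it could be made after the results have been seen.

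**Working it through.** **1. Sequence of events.** The plan states no figure on this point, so the check is the order of events.

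| Event | Time | Source |
|---|---|---|
| First Visit 2 complete | week 0 | Section 5.0 |
| Envelope may be opened | week 0 or later, no date given | Section 6.0 |
| 6-week clock starts | week 0 | Section 5.0 |
| Repeat Visit 2, if needed | after week 6, before training | Section 5.0 |

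The event that permits opening is the event that starts the clock. A repeat Visit 2 therefore always falls more than six weeks after opening became permissible. If the envelope is opened promptly, the repeat is a post-allocation measurement. If it is held until just before training, it is not. The text allows both.

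**2. Which measures are exposed.** Visit 2 carries the 6-minute walk, submaximal walk, dynamometry, pulse wave velocity and blood sample. The first three are the more open to effort or encouragement. Visit 1 measures, such as cutaneous vascular conductance, are not repeated under this rule. The feasibility outcomes in Section 3.1 do not use these baselines.

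**3. How easily six weeks is passed.** Section 6.0 says: "Open recruitment will occur for fixed periods (4-6 weeks"), and women train in waves. For the first woman in a wave:

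wait = (last recruitment date − first recruitment date) + (difference in their processing times) + (lag from last Visit 2 to session 1)

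Processing covers consent review, physician clearance, Visit 1, the washout of at least 7 days and Visit 2. Every woman goes through it, so with equal processing times that term is zero. If a wave fills over one whole recruitment window (an assumption) and there is no lag, the wait is about 4 to 6 weeks at most. The repeat is triggered only above 6 weeks:

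- 6-week window: 6 − 6 = 0, so any further delay passes the limit.
- 4-week window: 6 − 4 = 2, so more than 2 further weeks are needed.

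**4. Size, for illustration.** Let q be the share of women whose baseline is re-measured with the arm known, and s the resulting between-arm shift in baseline, in SDs of the change score. Both are assumptions; the documents give neither. Bias in d = q × s, supposing the repeat is used as the baseline.

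| q | s = 0.2 | s = 0.5 |
|---|---|---|
| 10% | 0.02 | 0.05 |
| 25% | 0.05 | 0.125 |
| 50% | 0.10 | 0.25 |

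Section 2.2 anticipates a small to medium effect, which Section 12.0 defines as d = 0.2 to 0.5. The approximate standard error of d is √(2/n) with n per arm: √(2/18) = 0.33 for the 36 women in Section 6.0, and √(2/12) = 0.41 for the 24 in Section 3.1.

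**The case against.** **The order is already stated.** Section 6.0 says baseline assessments precede randomisation, and Section 5.0 calls the repeat a baseline visit. A sensible team could read the two together and hold the envelope. This is fair, and it is why the point is what the plan allows. But the concealment sentence names only completion of Visits 1-2, so a team following it literally may open the envelope then.

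**The effect may be negligible.** At 10% affected, the bias of 0.02 to 0.05 is small beside a standard error of 0.33 to 0.41. Without a placebo, women also know their arm at the post-intervention walk, which envelope timing cannot change. Both statements are true. They limit the importance of the point but do not justify leaving open a route that wording can close.

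**Stronger readings that a reader might infer.** None of these is supported:

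- That every arm is revealed at Visit 2. The documents give an earliest time for opening, not a date.
- That the last recruit's washout lengthens the first recruit's wait. Both women have a washout, so it cancels.
- That the repeat necessarily replaces the first Visit 2. The purpose of the 6-week rule suggests this, but no section says it.
- That early allocation unfairly lowers the figure of 20 of 24 randomised women completing. Section 3.1 makes retention a primary outcome, so a loss before session 1 is legitimate feasibility information, and moving such losses out of the denominator is debatable.

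**Conclusion.** The point holds as a gap in allocation timing. Following the plan as written permits an effort-dependent baseline to be measured with the arm known, and the analysis baseline is undefined when Visit 2 is repeated. The documents do not show that this will occur or how often. Exceeding six weeks is plausible but needs some delay beyond the recruitment spread.

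On the assumed values, the bias in d runs from trivial (0.02) to as large as the lower half of the anticipated effect range (0.25), in a direction that cannot be stated. It touches the secondary and exploratory comparisons that rest on Visit 2 and leaves the primary feasibility outcomes alone. The change is worth making because it is specific and costs almost nothing, not because the likely bias is large.

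**What to change.** - **Sections 5.0 and 6.0:** state that each envelope stays sealed until the wave's training start date is fixed and any repeat Visit 2 that this date requires has been done. The juice hand-out in Section 8.0 already follows randomisation, so it would move with the opening.
- **Section 12.0:** define the analysis baseline as the last measurement taken before the envelope is opened. If the start slips after opening and Visit 2 is repeated, that repeat would be reported descriptively and would not replace the baseline.
- **Records:** log the date each envelope is opened and the date of every Visit 2, so that the order can be verified.

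**Cost.** A wording change in three sections and two dates per woman. No visit is added and no procedure changes. The drawback is that women learn their arm later, nearer to the first session. Where a start slips after opening, the retained baseline will be more than six weeks old. Any drift in fitness over that interval adds noise, but it is a smaller concern for the comparison than a baseline taken with the arm known.

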## 6.0 Enrollment/Randomization

The present study will rely on participant self-referral in response to recruitment materials. Participants will be recruited from the local community through approved flyers and/or approved written scripts (See Attachments) via:

- social media
- newspaper ads
- physical postings with permission from local establishments
- or sent to the email address of local organizations with the intent that the approved recruitment flyer will be forwarded to a member of their organization. Additionally, study details will be registered through the Indiana CTSI All IN for Health website. Open recruitment will occur for fixed periods (4-6 weeks).

Additional recruitment efforts include referral from the Indiana CTSI All IN for Health Volunteer Registry.

Subjects will be identified from the Indiana CTSI volunteer registry Protocol Number 1105005444. This website is created for interested individuals to contact us and sign up to receive information about ongoing studies and is supported by the Indiana CTSI. Persons in this registry have provided their health information for the purposes of being matched to appropriate research studies. The registry volunteers have signed an electronic consent/authorization so that their information can be used and they can be contacted for this reason.

The All IN manager will send an email message (see provided email text) to participants describing the study and asking them to reach out to the study team directly if they are interested in hearing more about the study.

Individuals expressing interest in the study will contact research personnel by telephone and /or email. If, by email, an agreed upon time to speak over the phone will be determined. During the phone call, research personnel will adhere to a scripted telephone screen wherein additional information detailing the inclusion/exclusion criteria, study procedures, requirements, and risks will be covered.

Based on participant responses to the questions, research personnel will determine preliminary eligibility for an on-site visit. If it appears the participant meets the preliminary eligibility, an on-site visit will be scheduled, and a consent form will be mailed / emailed to the participant for their consideration and review. After the study participant has had several days to review the consent form, research personnel will call the participant to answer any further questions regarding the consent form. Participants will be enrolled in small ( $n = 9$ ) cohorts or "waves" to facilitate social support and adherence to the supervised exercise training sessions. We anticipate having 9 waves to successfully reach our target  $n$ . This assumes that each wave will have 4 participants, hence, 4 participants x 9 waves = 36 total participants.

At the on-site screening visit, research personnel will once again cover inclusion/exclusion criteria, study procedures, requirements, and risks. Following written informed consent, participants will have their body weight and standing height measured to determine their body mass index (i.e., 25.0-39.9 kg/m^2). Current prescription drug use will be recorded by having

participants physically bring their prescription labels or medication bottles to the testing site. Additionally, participants will complete a Medical History Questionnaire (see attachments).

Written authorization will be obtained from consented participants to allow research personnel to contact the participant's primary care physician to receive physician's clearance prior to study testing visits. The physician will be asked to provide their assent or dissent for their patient to participate in the exercise testing protocols and supervised group exercise sessions involved with this study. They will have the option to indicate any modifications that may be necessary for the patient to participate safely. The Physician Clearance Form (see attachments) will be faxed to the patient's physician following the screening visit.

Participants will perform baseline assessments (**Visits 1-2**) prior to randomization. Subsequently, participants will be randomly selected to: 1) control (EX only) or 2) BR+EX. Group allocation will be determined at random using a computer-based number generator in blocks of 2 to ensure equal between-group distribution (i.e.  $n = 2$  Ex only;  $n = 2$  BR+EX). Each number will be kept in a sealed envelope until completion of **Visits 1-2**.

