#### **3.2 Secondary Outcome Measures**

**2a.** The distance (feet) covered during a 6-minute walk test at baseline prior to the intervention and following BR+EX is the main secondary outcome of interest. To confirm the relationship of the functional 6-minute walk test to aerobic fitness, measures of oxygen consumption (ml/kg/min or L/min), heart rate (bpm), and blood pressure (mm Hg) will be taken during constant speed walking at a typical walking pace prior to the 6-minute walk test. Additionally, functional mobility will be assessed by analyzing triaxial movement patterns from an accelerometer worn on the non-dominant hip during the 6-minute walk test.

The BR+EX intervention will be considered successful in the event that there is a statistically significant increase in 6-minute walk distance (feet) along with a decrease in oxygen consumption (ml/kg/min or L/min), decrease in exercising heart rate (bpm), improvement in heart rate recovery following exercise (post exercise heart rate – heart rate 1 min, 2 min after exercise (bpm)), decrease in exercising blood pressure (mm Hg), decrease in post-exercise blood pressure (mm Hg), and/or improvement in gait function (i.e. preferred walking speed, center of mass characteristics) from baseline to post-intervention above any improvement seen in EX.

**2b.** Percent changes in brachial artery diameter (%), cutaneous vascular conductance (%), and pulse wave velocity (m/s) at baseline prior to the intervention and following BR+EX are secondary outcomes of interest, representing changes in endothelial dependent vasodilation. A non-invasive technique of flow mediated dilation of the brachial artery using ultrasound imaging will be used to assess the percent change in vessel diameter following occlusion. A local heating protocol using non-invasive Laser Doppler flowmetry in conjunction with blood pressure measurements will be used to obtain measures of red blood cell (RBC) flux and mean arterial pressure (MAP) to calculate cutaneous vascular conductance (RBC flux/ MAP). The velocity of the pulse wave traveling from the carotid to femoral artery will be assessed non-invasively using tonometry.

A statistically significant increase in the percent change in brachial artery diameter (%), cutaneous vascular conductance (%), and/or a decrease in pulse wave velocity (m/s) in BR+EX above any improvement observed in EX from baseline to post-intervention will be considered a successful outcome.

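### Small fixed blocks with no stated rule for opening envelopes: between 0% and 50% of arms may be certain beforehand, and allocation is not clearly held until after a repeated baseline Visit 2

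*Combined protocol and SAP*

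**What the plan says.** On allocation, Section 6.0 states: "Group allocation will be determined at random using a computer-based number generator in blocks of 2 to ensure equal between-group distribution". It then illustrates this as two women on exercise only and two on beetroot plus exercise. That fits one block of 4, or two blocks of 2, as well as it fits a wave of four women. On concealment it states: "Each number will be kept in a sealed envelope until completion of" Visits 1-2. It does not say whether envelopes are opened as each woman finishes or together for a wave, who holds them, or that block size varies.

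On waves, the same section gives two sizes: "Participants will be enrolled in small ( $n = 9$ ) cohorts or" waves, and then "This assumes that each wave will have 4 participants, hence, 4 participants x 9 waves = 36 total participants". The exercise training description in Section 7.0 also points to about four.

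On visibility of the arm, the control in Section 5.0 is exercise alone with no placebo. Section 8.0 says that "subjects in the BR+EX group will receive a 4-week supply of beetroot juice". No masking of staff or participants is described.

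On the baseline itself, Section 3.2 says the distance "covered during a 6-minute walk test at baseline prior to the intervention and following BR+EX is the main secondary outcome of interest". That walk is done at Visit 2. Section 5.0 adds "Exercise training will occur no more than 6 weeks following baseline Visit 2", and "Subjects will be asked to repeat baseline Visit 2 before initiating exercise training in the event >6 weeks lapses".

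**The concern.** Sealing the numbers until baseline is complete shows that the plan wants baseline measurement to be unaffected by the arm. A small fixed block can defeat that. Once the earlier members of a block have been allocated in plain sight, the remaining arm or arms can be deduced without opening anything.

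If an assessor can deduce a woman's arm before she finishes Visit 2, her baseline 6-minute walk and knee-extension tests are taken with the arm foreseen. Both depend on effort and encouragement. Section 3.2 judges the walk on improvement from baseline beyond that seen with exercise alone, so a baseline error that differed by arm would enter any comparison of change directly. The secondary and exploratory effect sizes are the ones Section 12.0 wants for planning a larger trial.

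A second route does not depend on block size. If a woman is allocated after her first Visit 2 and then has to repeat it because training starts late, the new baseline may be recorded with her arm known to her and to staff.

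**Working it through.** **Inputs**
- Block size: 2 as worded, 4 as the gloss allows (Section 6.0). Ratio 1:1.
- Waves: 4 × 9 = 36, which reproduces the figure in Section 6.0.
- Randomized women in the success criterion: 24 (Section 3.1); 20/24 = 83.3%, which agrees with the stated 83%.
- How envelopes are opened: not stated, so each possibility is worked through.

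The plan gives no predictability figure of its own. Call an arm certain if, given the arms already opened, only one arm is left in its block. Assume that staff know the block size and the earlier arms.

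**Opened one at a time, blocks of 2.** The second of each pair is always certain.
- Certain: 1/2 = 50%, that is 24 × 0.5 = 12 of 24, or 36 × 0.5 = 18 of 36.
- Best guess correct: (0.5 + 1)/2 = 75%, against 50% by chance.

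**Opened one at a time, blocks of 4.** There are 6 balanced sequences. The fourth arm is always certain. The third is certain when the first two match, which happens in 2 of the 6.
- Certain: (1 + 1/3)/4 = 33.3% on average, that is 8 of 24 or 12 of 36.
- This is an average. A single block has one or two certain arms, 25% or 50%. Over 24 women (6 blocks) the count runs from 6 to 12; over 36 (9 blocks), from 9 to 18.
- Best guess correct: (1/2 + 2/3 + 2/3 + 1)/4 = 2.833/4 = 70.8%.

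**Opened two at a time, in step with the block.** Blocks of 2: 0%. Blocks of 4: the second pair is certain in 2 of 6 sequences, so (2/6) × (2/4) = 16.7%.

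**Whole wave of 4 opened together.** 0% for either block size, because no block is part-opened when the wave is allocated.

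**Whole wave opened together, but waves of 3 drawn from one continuous list.** Blocks then straddle waves. Blocks of 2: one position in every six is certain, 1/6 = 16.7%. Blocks of 4: over a cycle of 12 positions, 1 + 2/3 are certain, so 1.667/12 = 13.9%. Reaching 0% therefore also requires that no block is carried into the next wave.

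**Repeat of Visit 2.** Section 6.0 releases the number on completion of Visits 1-2, and Section 5.0 places randomization after those visits. Section 5.0 then requires a repeat of Visit 2 if more than 6 weeks pass before training. No sentence says that allocation waits for the repeat. On a plain reading a woman could be allocated, wait more than 6 weeks, and then give a new baseline walk.

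**The case against.** The strongest reply is that the 50% and 33% figures need one-at-a-time opening, which the plan never states. Women are enrolled in waves, the arithmetic in Section 6.0 gives four per wave, and the 2 + 2 gloss equals one such wave. If each wave is opened together, the exposure is already 0% and only the wording needs attention. This stands, and it is why the result is a range.

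A reader might infer that half of all arms are predictable, or that women could be selected into an arm. The documents support neither. Self-referral, consent, physician clearance and both baseline visits precede a woman's own envelope. With waves of 4, blocks of 2 or 4 stay inside a wave. What remains is foreknowledge at Visit 2, and only if visits within a wave are staggered; their spacing is not given.

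A reader might also infer that the 6-minute walk results will be biased. The walk follows standard procedures (Section 7.0), nothing shows that an assessor would shift it, and there is no basis for putting a size on any shift. In addition, participants will know their arm at follow-up whatever the block size, and Section 12.0 disclaims confirming efficacy. These points limit the severity. They do not make the current wording preferable.

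On the repeat visit, completion of Visits 1-2 can be read to include a repeated Visit 2. That reading is possible but not stated, and the point is separate from block size.

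**Conclusion.** The concern holds in a limited form. The share of arms certain before opening lies between 0% and 50%, depending on an opening procedure that the plan leaves out. Under one-at-a-time opening it is 50% with blocks of 2 and 33% on average with blocks of 4; with a whole wave of 4 opened together it is 0%. The upper figures assume that staff know the block size and the earlier arms. That the trial is unmasked is inferred from the design, since the documents do not use the word.

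The exposure is confined to effort-dependent baseline tests at Visit 2, chiefly the main secondary outcome. The feasibility criterion of 20 completers among 24 randomized is little affected. The repeat-visit gap is a second, independent point that holds for any block size. Severity: minor to moderate.

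**What to change.** In Section 6.0, replace the blocks of 2 with one randomly permuted balanced draw per wave (2:2 for a wave of 4). Make the draw after the wave list is closed and every member has completed Visit 2 and any repeat. Release all arms together and carry no block into the next wave. Have an existing person who does no assessments hold the list.

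**Odd-sized waves.** Choose the arm of the extra place at random in the first odd wave and give it to the opposite arm in the next, then start again. Overall imbalance then never exceeds 1. Drawing the extra place independently each time would let imbalance build up. As an illustration, assume 24 women in 8 waves of 3: the chance of a difference of 4 or more is 2 × (1 + 8 + 28)/256 = 74/256 = 29%. Odd waves are plausible, since 24 women over 9 waves average 2.7.

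**Repeat visits.** State that completion of Visits 1-2 includes any repeated Visit 2. If a repeat still falls after the draw, flag it and use the pre-draw Visit 2 in a sensitivity analysis.

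**Wave size.** Reconcile n = 9 with 4 in Section 6.0, because the draw depends on it.

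**Cost.** Protocol wording and no new staff. If per-wave opening is already intended, the change only writes it down. The downside is that early finishers may wait for the last member of the wave to learn their arm, and a few may pass the 6-week limit and need a repeat Visit 2, which includes a blood draw and maximal knee extensions. The 6-week limit runs from Visit 2 to the start of training, not to allocation, so where a wave starts training together the later draw adds no delay. The length of any wait cannot be worked out from the documents. The change removes predictability only; it does not mask follow-up assessment.
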